2. PDQ-39
3. Patient Global Impression-Severity (PGI-S)
4. Clinician Global Impression of Severity (CGI-S)
5. MDS-UPDRS Part II
6. MDS-UPDRS Part III
7. MDS-UPDRS Part I
8. Non-Motor Symptom Scale (NMSS)
9. Complete Spontaneous Bowel Movement score (CSBM)
10. ESS (Epworth Sleepiness Scale)
11. Schwab and England ADL Scale
12. Patient Assessment of Upper GI Disorders Severity Index (PAGI-SYM)
13. Patient Assessment of Constipation Quality of Life (PAC-QoL)
14. Patient Assessment of GI Disorders Severity Quality of Life (PAGI-QoL)

## 2.5 EXAMINATION OF SUBGROUPS

Subgroup analysis of the proportion of participants who discontinue treatment up to Week 12 will be made to assess consistency of the intervention effect across the subgroups:

- Above and below median baseline UPDRS part III
- Age group  $< 65$  vs  $\geq 65$
- Sex: female vs male
- Baseline CSBM  $\leq 3$  vs CSBM  $> 3$

If the number of participants is too small ( $< 10\%$  in a subgroup), then the subgroup categories may be redefined prior to unblinding the study. Descriptive statistics will be presented.

## 2.6 POOLING OF CENTERS

This study is a multicenter study with approximately 32 sites planned across the United States. Decisions regarding pooling of data across sites that had low enrollment will be made and documented prior to treatment unblinding.

# 3 PRIMARY, SECONDARY AND OTHER VARIABLES

## 3.1 PRIMARY EFFICACY ENDPOINT

There are no primary efficacy variables in this study. The primary tolerability endpoint is the proportion of participants who discontinue treatment up to Week 12.

Safety endpoints will be reported descriptively (see Section 3.4).

## 3.2 SECONDARY EFFICACY ENDPOINTS

The Movement Disorder Society - Unified Parkinson's Disease Rating Scale (MDS-

UPDRS) is used for several of the endpoints below. It is a four-part scale, with each item in the scale rated as 0-4, where 0=normal, 1 = slight, 2 = mild, 3 = moderate, and 4 = severe.

Change from baseline is calculated for each endpoint as *Value at Visit X - Value at baseline*.

### 3.2.1 MDS-UPDRS Parts II + III

This endpoint combines the results from Part II (Motor Aspects of Experiences of Daily Living), which has 13 items, and Part III (Motor Examination), which has 33 items. Part II and Part III scores are totaled, then added together, with a range of 0 – 184.

Change from baseline (CFB) will be calculated for Visits 2 (Week 4), 3 (Week 8), 4 (Week 12), and 5 (Safety follow-up). A negative CFB reflects improvement.

### 3.2.2 Parkinson's Disease Questionnaire (PDQ-39)

The PDQ-39 is a self-administered questionnaire that assesses how often people affected by PD experience difficulties across 8 dimensions of daily living, including mobility (10 items), activities of daily living (6 items), emotional well-being (6 items), stigma (4 items), social support (3 items), cognition (4 items), communication (3 items), and bodily discomfort (3 items).

Each item is scored as one of 5 ordered response categories. Each dimension score is summed then divided by the number of items and multiplied by 100 to get a percentage score ranging from 0 to 100, with lower scores indicating better health and higher scores more severe symptoms. The PDQ-39 is scored by taking the sum of the 8 scale scores, divided by the number of dimensions (8), which yields a score between 0 and 100 ([Hagell 2009](#)).

CFB will be calculated for Visits 2 (Week 4), 3 (Week 8), 4 (Week 12), and 5 (Safety follow-up). A negative CFB reflects improvement.

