9.1.4. Parkinson’s Disease Questionnaire (PDQ-39)

The PDQ-39 is a self-administered questionnaire that assesses how often people affected by PD experience difficulties across 8 dimensions of daily living, including mobility (10 items), activities of daily living (6 items), emotional well-being (6 items), stigma (4 items), social support (3 items), cognition (4 items), communication (3 items), and bodily discomfort (3 items). (Peto et al 1995). It also assesses the impact of PD on specific dimensions of functioning and well-being. The PDQ-39 is scored on a scale of 0 to 100, with lower scores indicating better health and higher scores more severe symptoms.

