## 1 INTRODUCTION

This study is being conducted for the clinical development of IKT-148009 (also known as Risvadotinib) for Parkinson's disease (PD). The purpose of this statistical analysis plan (SAP) is to describe the procedures and the statistical methods that will be used to analyze and report results based on Protocol IKT-148009-201 version 6.4, dated October 19, 2023.

The document may evolve over time to reflect protocol amendments, regulatory discussions, and other important changes. However, the SAP will be finalized, approved by the Sponsor, and placed on file before the database is locked and the study unblinded. In case of any differences between the SAP and the protocol, the SAP will be the final determinant. Deviations from the final approved plan will be noted in the clinical study report.

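### The PDQ-39 scoring formula in SAP 3.2.2 cannot give its stated 0-100 range: with integer item codes the second-ranked endpoint runs 0-400 or 100-500

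*SAP*

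**What the plan says.** SAP 3.2.2 lists eight PDQ-39 dimensions with their item counts. On coding it says only: "Each item is scored as one of 5 ordered response categories". The dimension score is "summed then divided by the number of items and multiplied by 100 to get a percentage score ranging from 0 to 100". The summary score is the sum of the eight dimension scores divided by eight, "which yields a score between 0 and 100".

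Protocol 9.1.4 names the same target scale and gives no formula: "The PDQ-39 is scored on a scale of 0 to 100, with lower scores indicating better health".

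SAP 2.4 places PDQ-39 second of 14 in the testing order; Protocol 5.2 had it eleventh. SAP Section 6 discloses that the order changed. On precedence, SAP Section 1 states: "In case of any differences between the SAP and the protocol, the SAP will be the final determinant".

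**The concern.** The formula and the range in the same SAP sentence do not agree. Dividing by the number of items gives a mean item score. Turning that into a percentage also requires division by the highest possible item score, and that divisor is missing.

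The reported magnitude of a prominent endpoint is at stake. SAP 4.2.3 calls for LS means, differences from placebo and 95% confidence intervals for PDQ-39, and Table 4-1 calls for baseline values of the total and all eight dimensions. If the formula is programmed literally on integer codes, all of these come out on a scale that neither document intends. A programmer who notices values above 100 has to choose a correction that the SAP does not specify, and the right one depends on item codes that the SAP does not give.

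**Working it through.** **Inputs**

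- Dimension formula (SAP 3.2.2): item sum ÷ k × 100, where k is the number of items in the dimension.
- Items per dimension (SAP 3.2.2): 10, 6, 6, 4, 3, 4, 3, 3. Check: 10 + 6 + 6 + 4 + 3 + 4 + 3 + 3 = 39.
- Summary (SAP 3.2.2): sum of the eight dimension scores ÷ 8.
- Item codes: not given. Three codings were tried as assumptions: 0-4, 1-5, and 0 to 1 in steps of 0.25.

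**Range of the formula as written**

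If every item takes the value c, the dimension score is (c × k) ÷ k × 100 = 100c. The number of items cancels, so all eight dimensions share one range. The summary, as their mean, has that range too.

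| Item coding (assumed) | Minimum | Maximum |
|---|---|---|
| 0-4 | 100 × 0 = 0 | 100 × 4 = 400 |
| 1-5 | 100 × 1 = 100 | 100 × 5 = 500 |
| 0 to 1 by 0.25 | 100 × 0 = 0 | 100 × 1 = 100 |

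The stated 0-100 is reproduced only in the third row.

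**Does the 0-to-1 coding fit the rest of the SAP?**

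SAP 3.2.2 has no missing-item rule for PDQ-39, so the default in SAP 2.3.5 applies. When no more than 20% of items are missing, the mean of the answered items is rounded up to a whole number and imputed. With 0-to-1 codes, any non-zero mean would round up to 1, the worst category. Take mobility (10 items) with nine items answered at 0.25 and one missing. The imputed value is 1, and the score is (9 × 0.25 + 1) ÷ 10 × 100 = 32.5. The nine answered items alone give 0.25 × 100 = 25. The default rule makes sense for integer item scores and distorts the data under 0-to-1 coding.

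**Size of the error**

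On a 0-100 scale, a dimension score with 0-4 codes is sum ÷ (4k) × 100. The ratio of the written formula to this is [sum ÷ k × 100] ÷ [sum ÷ (4k) × 100] = 4. A 3-point difference, chosen only for illustration, prints as 3 × 4 = 12. With 1-5 codes, levels are also raised by 100, but the shift cancels in change from baseline.

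**Effect on the tests**

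Multiplying both the response and the baseline covariate by 4 multiplies each estimate and its standard error by 4, so the test statistic stays the same. One simulated data set (30 per group, random item responses, two-sample t test on the change in the summary score) showed this:

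| Scoring | Difference | t | p |
|---|---|---|---|
| As written, 0-4 codes | 19.28 | 2.004 | 0.0497 |
| As written, 1-5 codes | 19.28 | 2.004 | 0.0497 |
| Divided by 4 × items, 0-4 codes | 4.82 | 2.004 | 0.0497 |

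**Range after correction**

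- Codes 0-4, sum ÷ (4k) × 100: 0 to 100.
- Codes 1-5, sum ÷ (5k) × 100: 20 to 100, so dividing by the maximum alone is not enough.
- Codes 1-5, (sum − k) ÷ (4k) × 100: 0 to 100.

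**The case against.** The strongest reply is that this cannot change any conclusion the trial tests. The error is a constant factor, so p-values and every step of the hierarchy are unaffected, and rank 2 adds no testing risk. PDQ-39 is a secondary endpoint in a study with no primary efficacy endpoint. The intended scale is stated twice in SAP 3.2.2 and once in the protocol, so scores above 100 would be noticed, and dividing differences and limits by 4 would restore them. The 0-400 and 100-500 ranges also rest on assumed codes. Finally, prescribing 0-4 codes settles a point the documents leave open: if the data are captured as 1-5, dividing the raw sum by 4 × items gives 25 to 125.

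Much of this stands. Inference is unaffected, the ranges are conditional on the coding, and a literal derivation would probably be noticed. The conflict lies within SAP 3.2.2; the two documents agree on 0-100. None of this makes the formula right. Detecting the problem does not settle the remedy, because the correction differs between 0-4 and 1-5 codes. The point about capture coding is met by stating the codes and recoding where needed.

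**Conclusion.** The concern holds. The written formula and its stated range cannot both be followed with integer item codes. PDQ-39 dimension scores and the summary index would run 0-400 (codes 0-4) or 100-500 (codes 1-5). Changes, LS mean differences and confidence limits would be four times their 0-100 values, and with 1-5 codes the levels would also carry an offset of 100. P-values and the hierarchical decisions are unchanged.

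This rests on integer coding, which the SAP does not state but which its default imputation rule presupposes. The one coding that rescues the formula, 0 to 1 in quarter steps, is also unstated and works badly with that rule. Nothing elsewhere in either document repairs the formula. The damage is to reported effect sizes, clinical interpretation and reproducibility. Because the SAP governs and gives this endpoint second rank, it should be corrected before database lock and unblinding.

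**What to change.** Replace the scoring sentence in SAP 3.2.2 with a rule that states three things:

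- Items are coded 0-4.
- Dimension score = sum of item scores ÷ (4 × number of items) × 100.
- Summary index = mean of the eight dimension scores.

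If the database captures items as 1-5, say that 1 is subtracted from each item before scoring. Equivalently, use (sum − minimum possible sum) ÷ (maximum possible sum − minimum possible sum) × 100, which gives 0-100 under either coding.

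The cost is one sentence in the SAP and the matching line in the derivation specification. No change to data collection, the model or the testing order is needed.

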### 3.2.3 Patient Global Impression – Severity (PGI-S)

The PGI-S is a single-item tool used to determine how severe a person feels their symptoms are at the time of questioning. It is based on a 5-point scale (none, mild, moderate, severe, and very severe).

CFB will be calculated for Visits 2 (Week 4), 3 (Week 8), 4 (Week 12), and 5 (Safety follow-up). A negative CFB reflects improvement.

### 3.2.4 Clinical Global Impression of Severity (CGI-S)

The CGI-S is a 7-point scale used to indicate how the clinician views the severity of the participant's illness at the time of questioning ([Guy, 1976](#)). The range includes 1 (normal), 2 (borderline ill, not ill at all), 3 (mildly ill), 4 (moderately ill), 5 (markedly ill), 6 (severely ill), and 7 (among the most extremely ill).

CFB will be calculated for Visits 2 (Week 4), 3 (Week 8), 4 (Week 12), and 5 (Safety follow-up). A negative CFB reflects improvement.

### 3.2.5 MDS-UPDRS Part II

This endpoint uses the results from MDS-UPDRS Part II (Motor Aspects of Experiences of Daily Living), which has 13 items. Item scores are totaled with a range from 0-52.

CFB will be calculated for Visits 2 (Week 4), 3 (Week 8), 4 (Week 12), and 5 (Safety follow-up). A negative CFB reflects improvement.

A total Part II score can be calculated if up to 2 items are missing, assuming that items are missing at random across participants ([Goetz et al, 2015](#)). The total score is calculated as the  $[(\text{sum of non-missing scores}) \times (\text{total number items})] / (\text{number of non-missing scores})$ .

### 3.2.6 MDS-UPDRS Part III

This endpoint uses the results from MDS-UPDRS Part III (Motor Examination), which has 33 items. Item scores are totaled with a range of 0-132.

CFB will be calculated for Visits 2 (Week 4), 3 (Week 8), 4 (Week 12), and 5 (Safety follow-up). A negative CFB reflects improvement.

A total Part III score can be calculated if up to and including 7 items are missing, assuming that items are missing at random across participants ([Goetz et al, 2015](#)). The total score is calculated as the  $[(\text{sum of non-missing scores}) \times (\text{total number items})] / (\text{number of non-missing scores})$ .

### 3.2.7 MDS-UPDRS Part I

This endpoint uses the results from MDS-UPDRS Part I (Non-Motor Aspects of Experiences of Daily Living), which has 13 items. Item scores are totaled with a range from 0-52.

CFB will be calculated for Visits 2 (Week 4), 3 (Week 8), 4 (Week 12), and 5 (Safety follow-up). A negative CFB reflects improvement.

If a single item is missing for a participant, a total Part I score can be calculated ([Goetz et al, 2015](#)), assuming that items are missing at random across participants. The total score is calculated as the  $[(\text{sum of non-missing scores}) \times (\text{total number items})] / (\text{number of non-missing scores})$ .

### 3.2.8 Non-Motor Symptom Scale (NMSS)

The NMSS is a 30-item scale divided into 9 domains as specified in [Table 3-1](#):

#### Table 3-1 Domains of the NMSS

Domain	Number of items	Question numbers
Cardiovascular/falls	2	1-2
Sleep/fatigue	4	3-6
Mood/cognition	6	7-12
Perceptual problems/hallucinations	3	13-15
Attention/memory	3	16-18
Gastrointestinal	3	19-21
Urinary	3	22-24
Sexual function	2	25-26
Miscellaneous	4	27-30

Each item is rated for frequency (1=rarely, 2=often, 3=frequent, 4=very frequent) and severity (0=none, 1=mild, 2=moderate, 3=severe) of symptoms ([Van Wamelen et al, 2020](#)). The item score for each item is calculated as frequency  $\times$  severity. Item scores within a domain are added for a total domain score, and the domain scores are added to get the total score. The total score has a range of 0 to 360, with higher scores reflecting higher symptomatic burden.

CFB will be calculated for Visits 2 (Week 4), 3 (Week 8), and 4 (Week 12). A negative CFB reflects improvement.

### 3.2.9 Complete Spontaneous Bowel Movement Score (CSBM)

The mean number of complete spontaneous bowel movements (CSBM) during the previous week will be assessed at baseline and at each Visit. A “spontaneous” bowel movement is a stool not induced by rescue medication such as laxative, enema, or suppository use during the previous 24 hour period. “Complete” refers to the sensation of complete evacuation of the stool.

Constipation is defined by the Rome IV criteria for constipation as less than or equal to 3 spontaneous bowel movements per week.

CFB will be calculated as the sum of unassisted diary values for Visits 2 (Week 4), 3 (Week 8), and 4 (Week 12). An increase (positive value) reflects improvement.

### 3.2.10 Epworth Sleepiness Scale (ESS)

The Epworth Sleepiness Scale (ESS) assesses sleepiness over time ([Johns 1991](#)). Patients and caregivers are asked to rate their likelihood of falling asleep during 8 daily activities, including reading, watching television, sitting in different situations, and driving.

Each item is scored as 0 (would never doze), 1 (slight chance of dozing), 2 (moderate chance of dozing), or 3 (high chance of dozing). Items are added for a total score ranging from 0 to 24. A high score reflects more severe sleep disorder.

---

If one or more items are missing, then the ESS is set to missing.

ESS will be obtained during Visit 1 (baseline) and Visit 4 (Week 12). Change from baseline will be calculated. A negative CFB reflects improvement.

### **3.2.11 Schwab and England Activities of Daily Living Scale (SE-ADL)**

The SE-ADL is a single item that assesses the difficulty that a participant has in completing daily activities. It ranges from 0% (bedridden) to 100% (completely independent). Scores are coded in increments of 10 (i.e., 100, 90, 80, ...). CFB will be calculated for Visits 2 (Week 4), 3 (Week 8), 4 (Week 12), and 5 (Safety follow-up). The participant value will be recorded. A positive value of CFB reflects improvement.

### **3.2.12 Patient Assessment of Upper GI Disorders Severity Index (PAGI-SYM)**

The Patient Assessment of Upper GI Disorders Severity Index (PAGI-SYM) measures symptom severity in patients with upper GI disorders. The participant is asked to rate the severity of symptoms over the last 2 weeks. There are 20 items in 6 subscales: heartburn/regurgitation, postprandial fullness/early satiation, bloating, nausea/vomiting, lower abdominal pain, and upper abdominal pain. Each item is rated from 0 (none) to 5 (very severe).

Each subscale is calculated as the mean of each non-missing item in the subscale. The PAGI-SYM score is calculated by taking the mean of all subscale scores ([Sebaratnam et al, 2021](#)). If > 50% of items in a subscale are missing, the subscale score and total score are defined as missing ([Tieglund et al, 2018](#)).

CFB will be calculated for Visits 2 (Week 4), 3 (Week 8), and 4 (Week 12). A negative CFB reflects improvement.

### **3.2.13 Patient Assessment of Constipation Quality of Life (PAC-QoL)**

The Patient Assessment of Constipation Quality of Life (PAC-QoL) assesses the effect that constipation has on daily life over the past 2 weeks. There are 28 items in 4 domains: physical discomfort (4 items), psychosocial discomfort (8 items), treatment satisfaction (5 items), and worries and discomfort (11 items). Each item is rated from 0 (not at all/never) to 4 (extremely/always). Items 25, 26, 27, and 28 should be scored reversed ([Marquis, et al, 2005](#)).

Each domain is calculated as the mean of the items in the domain. The total score is calculated as the mean of the 4 mean domain scores.

CFB will be calculated for Visits 2 (Week 4), 3 (Week 8), and 4 (Week 12). A negative CFB reflects improvement.

### 3.2.14 Patient Assessment of GI Disorders Severity Quality of Life (PAGI-QoL)

The Patient Assessment of GI Disorders Severity Quality of Life (PAGI-QoL) assesses the effect that GI problems have on daily life over the past 2 weeks. There are 30 items in 5 dimensions: daily activities (10 items, Q1-10), clothing (2 items, Q11-12), diet and food habits (7 items, Q13-20), relationship (3 items, Q20-22), and psychological well-being and distress (8 items, Q23-30). Each item is rated from 0 (none of the time) to 5 (all the time) ([De La Loge et al, 2004](#)).

Individual items are rated such that a higher score represents a worse outcome. However, each subscale score is taken as the mean of the items in each subscale, when all item responses are reverse-coded such that a higher score represents a better disease-specific quality of life. The PAGI-QOL summary score is calculated as the mean of all subscales ([Sebaratnam et al. 2021](#)).

In case of missing data, the subscale score is calculated when 50% or less of the items are missing for that scale. If >50% of items in a subscale are missing, the score is set to missing. If a subscale score is set to missing then the total score is also set to missing.

CFB will be calculated for Visits 2 (Week 4), 3 (Week 8), and 4 (Week 12). A negative CFB reflects improvement.

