9.1.10. Patient Assessment of GI Disorders Severity Quality of Life (PAGI-QoL)

The PAGI-QoL assesses the effect that GI problems have on daily life over the past 2 weeks. There are 30 items which are rated from 0 (none of the time) to 5 (all the time).

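### SAP 3.2.14 contradicts itself on the PAGI-QoL item map: the seven-item diet subscale is given eight questions, and Q20 sits in two subscales

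*SAP*

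**What the plan says.** SAP 3.2.14 describes the instrument as follows: "There are 30 items in 5 dimensions: daily activities (10 items, Q1-10), clothing (2 items, Q11-12"), then "diet and food habits (7 items, Q13-20), relationship (3 items, Q20-22"), and finally psychological well-being and distress with 8 items at Q23-30. Protocol 9.1.10 confirms the total, "There are 30 items which are rated from 0 (none of the time) to 5 (all the time"), but gives no subscales.

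Under SAP 3.2.14, items are reverse-coded, each subscale is the average of its items, and the summary score is the plain average of the five subscales. For incomplete questionnaires, "the subscale score is calculated when 50% or less of the items are missing for that scale". Above that limit the subscale is missing, and one missing subscale makes the total missing.

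PAGI-QoL is a secondary efficacy endpoint (SAP 1.2.3), is analysed by MMRM (SAP Table 4-3), and stands 14th of 14 in the testing order (SAP 2.4). No other section of either document maps questions to subscales; SAP Table 4-1 lists none for PAGI-QoL.

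**The concern.** A scoring program needs question numbers, and SAP 3.2.14 is the only place in the two documents that supplies them. Both documents let the SAP prevail where they differ (SAP section 1, protocol 5.4.1), so the protocol does not settle the matter. A program that follows the printed ranges will run without an error message, yet it will put Q20 into two subscales and average diet over eight questions. A program that follows the stated counts will not. Two analysts working in good faith could therefore derive different summary scores from the same data, and could disagree on whether a participant with missing answers has a score at all.

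**Working it through.** **Inputs.** All counts, ranges and scoring rules come from SAP 3.2.14. Protocol 9.1.10 supplies the 30-item total and the 0-5 item scale.

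**Step 1: reproduce the stated total.** The size of a range is last minus first plus one.

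| Subscale | Stated items | Stated range | Questions in range |
|---|---|---|---|
| Daily activities | 10 | Q1-10 | 10 |
| Clothing | 2 | Q11-12 | 2 |
| Diet and food habits | 7 | Q13-20 | **8** |
| Relationship | 3 | Q20-22 | 3 |
| Psychological well-being and distress | 8 | Q23-30 | 8 |
| Total | **30** | | **31** |

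The counts reproduce the stated 30. The ranges give 31 places for 30 distinct questions, and Q20 is the only question used twice. Four of the five ranges match their counts; diet does not.

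**Step 2: which single change reconciles the text?**
- Diet to Q13-19: the counts become 10, 2, 7, 3, 8, the total is 30, and there is no overlap. Everything stated is met.
- Relationship to Q21-22: the overlap goes and the total is 30, but diet has 8 items and relationship 2, against the stated 7 and 3.

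**Step 3: weights in the summary score.** A question's weight is the sum, over the subscales that contain it, of (1/5) × (1/number of questions in that subscale).
- Q20, ranges as printed: (1/5)(1/8 + 1/3) = 11/120 = 0.0917.
- Q20, diet as Q13-19: (1/5)(1/3) = 1/15 = 0.0667. The ratio is 0.0917/0.0667 = 1.375.
- Each of Q13 to Q19: 1/40 = 0.0250 as printed, against 1/35 = 0.0286.

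**Step 4: shift in the summary score, all items answered.** Let m be the mean of Q13-19 and q the value of Q20.
- Diet as printed is (7m + q)/8, which differs from m by (q − m)/8.
- Averaging over five subscales, the summary differs by (q − m)/40.
- Items run from 0 to 5, so |q − m| is at most 5 and the shift is at most 5/40 = 0.125 points per visit. Reverse-coding changes its sign, not its size.
- In a change from baseline, two such shifts are subtracted, so the extreme is 2 × 0.125 = 0.25.
- The between-arm difference in mean change moves by 1/40 of the between-arm difference in change of (q − m). If that difference were half a category (an assumption for scale only; the documents give no figure), the estimate would move by 0.5/40 = 0.0125.

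**Step 5: the 50% rule.** Suppose four of Q13-19 are missing and Q20 is answered.
- Seven items: 4/7 = 57% missing, so diet and the total are missing.
- Eight items: 4/8 = 50% missing, so both are scored, provided the other subscales can be.

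Up to three missing diet items are allowed under the stated count, and four under the printed range.

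**The case against.** The best reply is that this is one wrong digit, and that the plan does not prescribe double-counting. The stated counts and the stated 30 items both point to a map without overlap, and a careful programmer would notice the clash. That stands. A reader might infer from the ranges that the trial's PAGI-QoL score will double-count an item. The documents do not support that: they contain both rules and do not show which one was programmed.

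A reader might also take the 37.5% rise in Q20's weight as a sign of material bias. That does not follow either. The absolute ceiling is 0.125 points per visit, reached only if Q20 is at one end of its scale and all seven diet items are at the other. The same map would apply in every arm and at every visit, so nothing in it favours one arm automatically.

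The endpoint's position limits the stakes further. Under SAP 2.4, PAGI-QoL is formally tested for the high dose only if the 13 endpoints before it are significant, and for the lower doses only later in the same chain. Otherwise its result is descriptive. The missing-item example is also a narrow case, and neither document gives a rate of missing items.

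What the reply does not remove is the contradiction itself. It lies in running prose, has no sign of redaction or a broken table, and is in the only item map available.

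**Conclusion.** The contradiction is certain: 7 stated diet items against 8 listed questions, Q20 in two subscales, and 31 places against 30 items. Double-counting is conditional on the ranges, rather than the counts, being programmed. If they are, the consequence is small: the summary score stays within 0.125 points of the non-overlapping version at any visit when all items are answered, and in rare patterns of missing answers a participant gains a score that the stated count would withhold. The primary safety endpoints, the sample size and the leading efficacy endpoint are untouched.

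Reading diet as Q13-19 is an inference from the SAP's own counts. Neither the questionnaire nor the scoring source that the SAP cites was available, so that reading is the best one on the documents, not a confirmed one. This is a minor correction, worth making because it leaves a named secondary endpoint with a single derivation.

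**What to change.** In SAP 3.2.14, change the diet and food habits range to Q13-19 and leave relationship at Q20-22. Before finalising, confirm both against the instrument's scoring manual. State that the 50% missing-item rule uses the confirmed counts, which means seven items for diet if the manual agrees.

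SAP version 1.1 is dated 28 March 2025 and SAP 1.3.1 already reports enrolment in the past tense, so scoring code may exist; the documents do not say. If it does, check its item map and document any correction, preferably before unblinding. The cost is one wording change and, where code exists, a short check of one derivation. No data collection or design element changes.
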